**Table 4. Derivation Rules for Confirmed Best Overall Response per IMWG Response Criteria**

Scenario	Timepoint Response at:			BOR
	Assessment 1	Assessment 2	Assessment 3	
1	sCR	sCR		sCR
2	sCR	NE	sCR	
3	CR/VGPR/PR/MR/SD/PD c	sCR	sCR	
4	CR	sCR/CR		CR
5	sCR/CR	CR		
6	CR	NE	CR	
7	VGPR/PR/MR/SD/PD c	CR	CR	
8	VGPR	sCR/CR/VGPR		VGPR
9	sCR/CR/VGPR	VGPR		
10	VGPR	NE	VGPR	
11	PR/MR/SD/PD c	VGPR	VGPR	
12	PR	sCR/CR/VGPR/PR		PR
13	sCR/CR/VGPR/PR	PR		
14	PR	NE	PR	
15	MR/SD/PD c	PR	PR	
16	MR	sCR/CR/VGPR/PR/MR		MR
17	sCR/CR/VGPR/PR/MR	MR		
18	MR	NE	MR	
19	SD/PD c	MR	MR	
20	SD	No further assessments		SD a
21	SD	sCR/CR/VGPR/PR/MR/SD/PD c	No further assessments	
22	sCR/CR/VGPR/PR/MR	NE/ PD c or no further assessment	No further assessments	
23	PD c	sCR/CR/VGPR/PR/MR/SD	No further assessments	
24	PD c	PD (any reason) including PD after initiation of new anticancer therapy		PD
25	PD c	Participant died due to disease before further disease		

090177e1a0f4f44c\Approved\Approved On: 14-Jun-2024 22:12 (GMT)

Scenario	Timepoint Response at:			BOR
	Assessment 1	Assessment 2	Assessment 3	
		assessment (including death due to disease under study after initiation of new anticancer therapy)		
26	PD b	sCR/CR/VGPR/PR/MR/SD/NE/PD or no further assessments	No further assessments	
27	Death (due to disease under study) before initiation of new anticancer therapy			
28	Death (not due to disease under study)			NE
29	NE	No further assessment		
30	NE	NE/PD c	No further assessments	
31	PD c	NE	No further assessments	
EMD = extramedullary disease; IMWG = International Myeloma Working Group, sCR = stringent complete response, CR = complete response, PR = partial response, VGPR = very good partial response, SD = stable disease, PD = progressive disease, NE = not evaluable. a SD does not need to be confirmed. b PD due to EMD (includes any new lesion, increased extramedullary or paramedullary lesions, plasmacytomas), or bone marrow plasma cells does not need to be confirmed. c PD due to reasons other than EMD, or bone marrow plasma cells.				

## 6.2. Secondary Efficacy Endpoints

### 6.2.1. Complete Response Rate

CRR is defined as the proportion of participants with a sCR or CR per IMWG criteria as determined by investigator.

Point estimates of CRR will be calculated along with corresponding 2-sided exact 95% CIs using the Clopper-Pearson method.

### 6.2.2. Progression-free Survival

PFS is defined as the time from the date of first dose until confirmed PD per IMWG criteria as determined by investigator or death due to any cause, whichever occurs first. The rules for PD confirmation are described in [Table 4](#).

PFS will be calculated as follows:

$$\text{PFS (months)} = [\text{date of event or censoring} - \text{date of first dose} + 1] / 30.4375.$$

PFS will be censored as follows:

- For participants who do not have an event (confirmed PD per IMWG criteria or death due to any cause), censoring will occur on the date of the last adequate disease assessment;
- For participants who start a new anticancer therapy (as defined in [Section 5.2.6 in the master SAP](#)) prior to an event, censoring will occur on the date of the last adequate disease assessment before the new anticancer therapy;
- For participants with an event after a gap of 2 or more missing disease assessments, censoring will occur on the date of the last adequate disease assessment before the gap;
- Participants who do not have an adequate post-baseline disease assessment will be censored on the date of first dose of study intervention unless death occurs on or before the time of the second planned disease assessment (i.e.,  $\leq 70$  days after the date of first dose) in which case the death will be considered an event.

The censoring and event date options to be considered for the PFS analysis are presented in Table 5. Adequate post-baseline disease assessment is defined in [Section 5.2.10 in the master SAP](#).

**Table 5. Outcome and Event Dates for PFS Analyses**

Scenario	Date of Event/Censoring	Outcome
Progression or death 1. After at most 1 missing or inadequate post-baseline disease assessment or 2. $\leq 70$ days after date of first dose of study intervention	Date of progression or death	Event
Progression or death after 2 or more missing or inadequate disease assessments a	Date of last adequate assessment a documenting no PD prior to new anticancer therapy or missed disease assessments	Censored
Neither progression nor death		
New anticancer therapy given prior to PD or death		

a. If there are no adequate post-baseline disease assessments prior to PD or death, then the time without adequate assessment should be measured from the date of first dose of study intervention; if the criteria were met, the censoring will be on the date of first dose of study intervention.

PFS = progression-free survival; PD = progressive disease

Kaplan-Meier estimates (product-limit estimates) will be presented and displayed graphically where appropriate, together with a summary of associated statistics including the median PFS time with 2-sided 95% CIs. The CIs for the median will be calculated according to Brookmeyer and Crowley, 1982.

The PFS rate at 3, 6, 9, 12, 18, and 24 months (and in subsequent 12-month increments while there are participants still at risk) will be estimated with corresponding two-sided 95% CIs. The CIs for the survival function estimates at the timepoints defined above will be derived using the log(-log) method according to Kalbfleisch and Prentice  (conftype=loglog default option in SAS Proc LIFETEST). The estimate of the standard error will be computed using Greenwood’s formula. Frequency (number and percentage) of participants with each event type (PD or death) and censoring reasons will be presented along with the overall event and censor rates.

Reasons for censoring will be summarized according to the categories in Table 6. If a participant meets multiple definitions for censoring the list will be used to define the hierarchy.

**Table 6. PFS Censoring Reasons and Hierarchy**

Hierarchy	Condition	Censoring Reason
1	Start of new anticancer therapy before event.	Start of new anticancer therapy
2	Event after 2 or more missing or inadequate post-baseline disease assessment after date of first dose	Event after missing or inadequate assessments a
3	No event and [withdrawal of consent date ≥ date of first dose or End of study (EOS) = Participant refused further follow-up]	Withdrawal of consent
4	No event and lost to follow-up in any disposition page	Lost to follow-up
5	No event and [EOS present or disposition page for any EPOCH after screening says participant will not continue into any subsequent phase of the study] and no adequate post-baseline disease assessment	No adequate postbaseline disease assessment
6	No event and none of the conditions in the prior hierarchy are met	Ongoing without an event

a. More than 70 days after last adequate disease assessment.

The PFS time or censoring time and the reasons for censoring will also be presented in a data listing.

### 6.2.3. Duration of Response

DOR is defined, for participants with an objective response per IMWG criteria as determined by investigator, as the time from the first documentation of objective response that is subsequently confirmed, until the date of the first confirmed PD per IMWG criteria, or death due to any cause, whichever occurs first. The rules for PD confirmation are described in [Table 4](#).

DOR will be calculated as follows:

$$\text{DOR (months)} = (\text{date of event or censoring} - \text{first date of objective response} + 1) / 30.4375$$

090177e1a0f4f44c\Approved\Approved On: 14-Jun-2024 22:12 (GMT)

The censoring rules for DOR are as described for PFS in [Section 6.2.2](#), except that participants will not be censored for no adequate post-baseline assessment, as only participants with an objective response are included in the analysis of DOR.

If at least 3 participants across all dose levels achieve an objective response and subsequently have an event, DOR will be estimated using the same Kaplan-Meier method as described for PFS in [Section 6.2.2](#) and displayed graphically where appropriate. Otherwise only listings will be provided.

The DOR rate at 3, 6, 9, and 12 months (and in subsequent 6-month increments while there are participants still at risk) will be estimated with corresponding two-sided 95% CIs.

#### 6.2.4. Duration of Complete Response

DOCR is defined, for participants with a sCR/CR per IMWG criteria as determined by investigator, as the time from the first documentation of sCR/CR that is subsequently confirmed, until the date of first confirmed PD per IMWG criteria, or death due to any cause, whichever occurs first. The rules for PD confirmation are described in [Table 4](#).

DOCR will be calculated as follows:

$$\text{DOCR (months)} = [\text{date of event or censoring} - \text{first date of confirmed sCR/CR} + 1] / 30.4375$$

The censoring rules for DOCR are as described for DOR in [Section 6.2.3](#).

If at least 3 participants achieve a sCR/CR and subsequently have an event, DOCR will be estimated using the same Kaplan-Meier method as described for DOR in [Section 6.2.3](#) and displayed graphically where appropriate. Otherwise only listings will be provided.

The DOCR rate at 3, 6, 9, and 12 months (and in subsequent 6-month increments while there are participants still at risk) will be estimated with corresponding two-sided 95% CIs.

#### 6.2.5. Overall Survival

OS is defined as the time from the date of first dose until death due to any cause and will be calculated in months as follows:

$$\text{OS (months)} = [\text{date of death or censoring} - \text{date of first dose} + 1] / 30.4375$$

Survival status is expected to be collected irrespective of study intervention discontinuation or participant's request to discontinue study procedures. All participants who have not withdrawn consent for further participation in the study should be followed for survival until the end of the study. OS for participants not known to have died are censored on the date of last known alive.

OS time will be estimated using the same Kaplan-Meier method and displayed graphically as described for PFS in [Section 6.2.2](#). Median OS and 2-sided 95% CI will be provided. The OS rate at 12, 24, and 36 months (and in subsequent 12-month increments while there are participants still at risk) will be estimated with corresponding two-sided 95% CIs.

Frequency (number and percentage) of participants with death events and censoring reasons will be presented along with the overall event and censor rates. The event and censoring reasons are as follows:

- Death;
- Ongoing and no death;
- Withdrawal of consent;
- Lost to follow-up.

In addition, OS will be summarized with simple descriptive statistics (mean, standard deviation, minimum, median, and maximum) for duration of follow-up.

The OS time or censoring time and the reasons for censoring will also be presented in a listing.

#### **6.2.6. Time to Response**

TTR is defined, for participants with an objective response per IMWG criteria as determined by investigator, as the time from the date of first dose to the first documentation of objective response that is subsequently confirmed. For participants with EMD at baseline, MR or better (for those with target plasmacytomas) and CR or better (for those with non-target non-bone EMD only) cannot be confirmed until a post-baseline EMD assessment is performed and the date of confirmed response cannot be prior to the initial EMD assessment date.

TTR will be calculated in weeks as follows:

$$\text{TTR (weeks)} = (\text{date of first objective response} - \text{date of first dose} + 1) / 7$$

TTR will be summarized using simple descriptive statistics (mean, standard deviation, minimum, median, and maximum).

#### **6.2.7. Minimal Residual Disease Negativity Rate**

MRD negativity rate is defined as the proportion of participants with negative MRD (assessed by central lab) per IMWG sequencing criteria at any time from the date of first dose until the first documentation of confirmed PD, death or start of new anticancer therapy, whichever occurs first. The rules for PD confirmation are described in [Table 4](#).

CCI

The MRD negativity rate will be calculated along with the 2-sided 95% CI using the Clopper-Pearson method as follows:

- MRD negative with confirmed sCR/CR based on the Safety Analysis Set;
- MRD negative based on the subset who achieved confirmed sCR/CR in the Safety Analysis Set.

MRD negative based on the subset of MRD evaluable patients (achieve sCR/CR and have at least one MRD assessment)

### **6.3. Other Secondary Endpoints**

#### **6.3.1. Pharmacokinetic/Pharmacodynamics**

Pharmacokinetic parameter analyses will be based on the PK Analysis Set.

##### **6.3.1.1. Elranatamab**

PK data analyses will include descriptive summary statistics of the predose and postdose serum concentrations, and PK parameters of elranatamab by study visit and time point. Box and Whisker plots for predose elranatamab concentrations by study visit and PK parameters ( $C_{max}$  and  $AUC_{last}$ ) will be generated. Values below the limit of quantitation for elranatamab and other analytes will be treated as zero in the descriptive statistics calculations. For additional details on handling missing and BLQ values, please refer to [Section 5.3.1 in the master SAP](#).

In addition, the PK data from this study may be used to develop a population PK model. PK data from this study maybe pooled with other studies for population PK model development. The correlations between elranatamab exposure parameters and pharmacodynamic biomarker, efficacy and/or safety outcomes will be explored if data allows. The results of these modeling analyses will be reported separately from the clinical study report.

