## 5.2. General Methods

Unless otherwise specified, all analyses will be performed for Phase 1b and Phase 2 separately and with the cohort of RP2D in Phase 1b and Phase 2 combined.

For the Phase 1b part of the study, all analyses will be performed by dose level and with all dose levels combined. For sub-study A, participants on Dose levels 1 and 2 escalated to the next higher dose level(s) will be summarized with the dose level originally assigned.

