**Table 2. Study Intervention Dose Levels and Administration**

Dose Levels (DL)	Elranatamab	Nirogacestat
1 (starting dose level)	Priming Dose: 4 mg C0D1 SC Full Dose: 4 mg C1D1 SC, weekly thereafter b	100 mg PO BID continuous starting on C1D1 until response a
2	2 Step-up Priming Dose: 4 mg C0D1 SC / 8 mg C0D4 SC Full Dose: 12 mg C1D1 SC, weekly thereafter b	100 mg PO BID continuous starting on C1D1 until response a
3	2 Step-up Priming Dose: 12 mg C0D1 SC / 32 mg C0D4 SC Full Dose: 32 mg C1D1 SC, weekly thereafter b	100 mg PO BID continuous starting on C1D1 until response a
Nirogacestat De-Escalation Levels		
3A	2 Step-up Priming Dose: 12 mg C0D1 SC / 32 mg C0D4 SC Full Dose: 32 mg C1D1 SC, weekly thereafter b	100 mg PO QD continuous starting on C1D1 until response a
4A	2 Step-up Priming Dose: 12 mg C0D1 SC / 32 mg C0D4 SC Full Dose: 76 mg C1D1 SC, weekly thereafter b,c	100 mg PO QD continuous starting on C1D1 until response a
3B	2 Step-up Priming Dose: 12 mg C0D1 SC / 32 mg C0D4 SC Full Dose: 32 mg C1D1 SC, weekly thereafter b	50 mg PO QD continuous starting on C1D1 until response a
4B	2 Step-up Priming Dose: 12 mg C0D1 SC / 32 mg C0D4 SC Full Dose: 76 mg C1D1 SC, weekly thereafter b,c	50 mg PO QD continuous starting on C1D1 until response a

- a. For Dose levels 3A/3B and 4A/4B, nirogacestat will be adjusted to 50 mg QD continuous at time of confirmed VGPR. Once CR (or better) is confirmed, nirogacestat will be permanently discontinued. For all other dose levels, nirogacestat can be continued or adjusted based on this guidance, per investigator discretion. See Section 6.1.1.5.
- b. Starting at Cycle 7, if a participant has received QW dosing for at least 6 cycles and PR or better persisting for ≥2 months, dose interval will be changed from QW to Q2W. See Schedule of Activities.
- c. For participants on Dose levels 4A and 4B receiving CCI dosing, CCI the dose interval will be changed to CCI

090177e1a0f4f44c\Approved\Approved On: 14-Jun-2024 22:12 (GMT)

CCI

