## 5.2. General Methods

Unless otherwise specified, all analyses will be performed for Phase 1b and Phase 2 separately and with the cohort of RP2D in Phase 1b and Phase 2 combined.

For the Phase 1b part of the study, all analyses will be performed by dose level and with all dose levels combined.

See [Section 5.2 of the master SAP](#) for the detail of the general statistical methods.

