##### **6.3.1.2. Nirogacestat**

PK data analyses will include descriptive summary statistics of predose serum concentrations of nirogacestat by study visit and time point. Box and Whisker plots for predose serum concentrations of nirogacestat by study visit will be generated. PK data from this study maybe pooled with other studies for population PK model development. The correlations between nirogacestat exposure parameters and pharmacodynamic biomarker, efficacy and/or safety outcomes will be explored if data allows. The results of these modeling analyses will be reported separately from the clinical study report.

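### Predose elranatamab and nirogacestat concentrations are summarised by visit without separating regimens that the plan changes on response

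*SAP*

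**What the plan says.** **How troughs are displayed.** Sub-study A SAP 6.3.1.1 gives descriptive statistics of elranatamab concentrations by visit and time point, with "Box and Whisker plots for predose elranatamab concentrations by study visit". Section 6.3.1.2 mirrors this for nirogacestat: "Box and Whisker plots for predose serum concentrations of nirogacestat by study visit will be generated". The only further split is in Section 5.2, where for Phase 1b "all analyses will be performed by dose level and with all dose levels combined". Dose level there means the assigned level, not the regimen at sampling. Phase 2 has no such split.

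**How the regimens change.** Three rules in the Table 2 footnotes depend on response:

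- Elranatamab, all levels, from Cycle 7 after at least six weekly cycles: with "PR or better persisting for ≥2 months, dose interval will be changed from QW to Q2W". A further interval change on 4A and 4B is redacted and is not assessed here.
- Nirogacestat on 3A, 3B, 4A and 4B: "nirogacestat will be adjusted to 50 mg QD continuous at time of confirmed VGPR".
- Nirogacestat on the same four levels: "Once CR (or better) is confirmed, nirogacestat will be permanently discontinued". On levels 1, 2 and 3 the investigator may continue or adjust.

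**What is done with exposure.** Trough concentrations in selected cycles are the Phase 2 PK endpoint (3.2.3). Correlations of exposure with efficacy are exploratory and are reported outside the CSR. No exposure metric or time window is named.

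**The concern.** From Cycle 7, one visit can hold 14-day troughs from participants who qualified on response and 7-day troughs from those who did not. For nirogacestat, one visit can hold samples taken on 100 mg QD and on 50 mg QD within the same assigned level. Nothing in the PK rules separates them. The missing-data rule in master SAP 5.3.1 removes unreported samples, sampling-time deviations and anomalous values, and a trough drawn on time on a two-weekly schedule is none of these.

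Two readings are then at risk. A falling by-visit plot could be taken as a change in clearance or as an interaction between the drugs, when it may only reflect the share of participants who responded and were moved to a sparser schedule. And if a correlation with efficacy were to use late exposure, the dosing rule itself would push it towards lower exposure going with better response.

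The same SAP does handle the regimen change elsewhere. Section 6.6.3.1 sets planned elranatamab dose by weekly or two-weekly schedule and counts those who switched. Section 6.6.3.3 keeps planned response-driven nirogacestat decreases out of the dose-reduction counts. The distinction is not carried into the PK sections.

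**Working it through.** The plan states no figure on this point, so there is none to reproduce.

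**Inputs.** Full doses and switching rules: Sub-study A SAP Table 2. Planned dose per cycle: 6.6.3.1 and 6.6.3.2. Responder count for illustration: 38 of 50, the minimum meeting the dual criteria (5.1.1.2). Half-life, linear PK, between-participant variability and the share who switch are assumptions; the documents give none of them.

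**Step 1: planned dose before and after the change**

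| Drug and level | Before | After |
|---|---|---|
| Elranatamab 76 mg, per cycle | 76 × 4 = 304 mg | 76 × 2 = 152 mg |
| Elranatamab 32 mg, per cycle | 32 × 4 = 128 mg | 32 × 2 = 64 mg |
| Nirogacestat 3A/4A, per 28 days | 100 × 28 = 2800 mg | 50 × 28 = 1400 mg at VGPR, 0 at CR |
| Nirogacestat 3B/4B, per 28 days | 50 × 28 = 1400 mg | 1400 mg at VGPR (no change), 0 at CR |

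**Step 2: trough ratio.** Assume linear one-compartment PK at steady state, ignoring absorption, with r = exp(−7k) and k = ln 2 / half-life. The weekly trough is proportional to r/(1 − r) and the two-weekly trough to r²/(1 − r²). Their ratio is r/(1 + r), which is below 0.5 for any half-life.

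| Assumed half-life (days) | r | Two-weekly / weekly trough |
|---|---|---|
| 7 | 0.500 | 0.333 |
| 14 | 0.707 | 0.414 |
| 21 | 0.794 | 0.442 |
| 28 | 0.841 | 0.457 |

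**Step 3: effect on a visit mean.** Suppose nobody's PK changes, pre-switch troughs do not differ by response, and all 50 participants are still sampled. If a fraction f has switched, the visit mean is (1 − f) + f × ratio of its earlier value.

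- All 38 switched, f = 0.76: 0.24 + 0.76 × 0.333 = 0.49, up to 0.24 + 0.76 × 0.457 = 0.59.
- 60% of the 38 switched, f = 0.456: 0.544 + 0.456 × 0.333 = 0.70, up to 0.544 + 0.456 × 0.457 = 0.75.

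So the plotted mean drops by 25% to 51% through the schedule change alone.

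**Step 4: effect on a late-exposure correlation.** Log trough was simulated as normal and correlated with response, 1,500 repetitions per setting. The settings were trough ratio 0.20, 0.33 or 0.44; CV 40% or 80%; 60% or 100% of responders switched; and 38 responders with 12 or 4 non-responders still sampled. With no true exposure-response effect, three settings show the range:

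| Setting (non-responders, ratio, CV, switched) | Pre-switch mean r; rejected at 5% | Post-switch mean r; rejected at 5% |
|---|---|---|
| 12, 0.20, 40%, 100% | 0.00; 3.8% | −0.88; 100% |
| 12, 0.33, 40%, 60% | 0.00; 4.7% | −0.43; 94.5% |
| 4, 0.44, 80%, 60% | 0.01; 5.5% | −0.17; 17.7% |

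When responders truly had early log troughs 0.5 SD higher, the pre-switch mean r was +0.14 to +0.22. The post-switch mean r was negative in every setting, from −0.05 to −0.85. The direction follows from the rule that only responders switch; the size depends on the assumptions.

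**The case against.** The strongest case against has four parts.

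1. **Late sampling is unconfirmed.** Troughs are taken in selected cycles, and the schedule naming those cycles was not supplied. Elranatamab mixing cannot start before Cycle 7. This stands, and it makes the point conditional.
2. **These are descriptive and exploratory outputs.** No hypothesis or decision rule uses them, and the Phase 2 criteria use ORR only. The number switched to two-weekly dosing is tabulated, so a reader would know that a change occurred. This limits the importance, but a count of switchers does not let a reader separate the two sets of troughs.
3. **No late exposure metric has been chosen.** The correlations are run only if data allow. A population PK model using actual dosing could separate the regimens, and the priming-dose Cmax, Tmax and AUClast are untouched. This stands for the modelling, but that model is optional and would not correct the by-visit tables.
4. **Off-drug nirogacestat values are speculative.** Nothing supplied says that samples are drawn after permanent discontinuation or would be labelled predose. Values below quantification are set to zero but are excluded from geometric means. This stands; an explicit exclusion is only a safeguard.

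A reader might also infer two stronger points that the documents do not support. The first is that escalated participants are reported under a dose they have left, because master SAP 5.2 says "participants on Dose levels 1 and 2 escalated to the next higher dose level(s) will be summarized with the dose level originally assigned". That sentence is in the 2021 master SAP. The 2024 Sub-study A SAP restates the paragraph without it, and its cross-references (baseline summaries in master 6.5.1, which is 6.6.1 in the supplied master) suggest that a different master version is meant. The second is that the Phase 1b output pooled over dose levels hides the dose. It is produced in addition to the by-level output, so nothing is lost.

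**Conclusion.** The concern holds in conditional form. Followed as written, Sections 6.3.1.1 and 6.3.1.2 would pool weekly with two-weekly elranatamab troughs, and different nirogacestat doses, at any visit sampled after a response-driven change. Under the assumed PK the two-weekly trough is 33% to 46% of the weekly one for half-lives of 7 to 28 days, and it is below half whatever the half-life. A decline over visits could then not be read as a PK finding.

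The scope is narrower than it may seem. Elranatamab is spaced out, not stopped. The VGPR step lowers the nirogacestat dose only on 3A and 4A, because 3B and 4B already start at 50 mg QD. The CR stop covers 3A, 3B, 4A and 4B, and levels 1 to 3 are discretionary. A reader might infer that the planned exposure-efficacy analysis is already biased. The documents do not show that, because they choose no exposure window; the bias arises only if late or averaged exposure is used without modelling actual dosing.

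The ORR analysis and the Phase 2 decision are not affected. This is worth correcting in the SAP, but it is not critical.

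**What to change.** - In 6.3.1.1 and 6.3.1.2, summarise and plot predose concentrations by visit and by the dose and interval in force before the sample. For example, use separate rows for 76 mg weekly and 76 mg two-weekly elranatamab, and for nirogacestat 100 mg BID, 100 mg QD and 50 mg QD.
- State that any nirogacestat sample taken after permanent discontinuation is left out of the trough summaries.
- If exposure-efficacy correlations are run, use exposure from before the participant's first response-driven regimen change, or a model that takes actual dosing over time as input.

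The dosing data are already collected. Protocol 8.4.1 records the time of the last dose before each elranatamab PK sample, and the exposure summaries already need the schedule and dose for each participant. The cost is SAP wording, one derived regimen variable, and smaller numbers per row at later visits. Treatment does not change.
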